10.3.1.1.2. AEs

AEs will be tabulated using MedDRA preferred terms. The number and percentage of participants experiencing each specific AEs (All AEs, Grade 2 or higher, and SAEs) will be tabulated by severity and by relationship to study product. For the calculations in these tables, each participant's AEs will be counted once under the maximum severity or the strongest relationship to study product. AEs leading to withdrawal will also be summarized. AEs will be summarized for those that are treatment emergent during LA dosing separately from those that are treatment emergent during oral dosing and also for those that are treatment emergent across the entire treatment phase of the study (combining both LA and oral dosing).

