- Exacerbation of a chronic or intermittent pre-existing condition including either an increase in frequency and/or intensity of the condition.
- New conditions detected or diagnosed after study treatment administration even though it may have been present before the start of the study.
- Signs, symptoms, or the clinical sequelae of a suspected drug-drug interaction.
- Signs, symptoms, or the clinical sequelae of a suspected overdose of either study treatment or a concomitant medication. Overdose per se will not be reported as an AE/SAE unless it is an intentional overdose taken with possible suicidal/self-harming intent. Such overdoses should be reported regardless of sequelae.

Events NOT Meeting the AE Definition

- Any clinically significant abnormal laboratory findings or other abnormal safety assessments which are associated with the underlying disease, unless judged by the investigator to be more severe than expected for the participant's condition.
- The disease/disorder being studied or expected progression, signs, or symptoms of the disease/disorder being studied, unless more severe than expected for the participant's condition.
- Medical or surgical procedure (e.g., endoscopy, appendectomy): the condition that leads to the procedure is the AE.
- Situations in which an untoward medical occurrence did not occur (social and/or

convenience admission to a hospital).

- Anticipated day-to-day fluctuations of pre-existing disease(s) or condition(s) present or detected at the start of the study that do not worsen.

Cardiovascular Events (CV) Definition:

- Myocardial infarction/unstable angina
- Congestive heart failure
- Arrhythmias
- Valvulopathy
- Pulmonary hypertension
- Cerebrovascular events/stroke and transient ischemic attack
- Peripheral arterial thromboembolism
- Deep venous thrombosis/pulmonary embolism
- Revascularization

AEs of Special Interest:

Diarrhea

Participants with Grade 1 or 2 diarrhea may continue study treatment without interruption. Participants with diarrhea of any toxicity grade may be treated symptomatically with anti-motility agents; however, the recommended daily dose of the chosen anti-motility agent must not be exceeded. If symptoms persist or get worse on the recommended daily dose of the chosen anti-motility agent, then the anti-motility agent must be discontinued and consultation made with the Medical Monitor.

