
f. Other situations:
 
 • Medical or scientific judgment should be exercised in deciding whether SAE reporting is appropriate in other situations such as important medical events that may not be immediately life-threatening or result in death or hospitalization but may jeopardize the participant or may require medical or surgical intervention to prevent one of the other outcomes listed in the above definition. These events should usually be considered serious. 
Examples of such events include invasive or malignant cancers, intensive treatment in an emergency room or at home for allergic bronchospasm, blood dyscrasias or

convulsions that do not result in hospitalization, or development of drug dependency or drug abuse.

Recording AE and SAE

AE and SAE Recording

- When an AE/SAE occurs, it is the responsibility of the investigator to review all documentation (e.g., hospital progress notes, laboratory, and diagnostics reports) related to the event.
- The investigator will then record all relevant AE/SAE information in the CRF.
- It is **not** acceptable for the investigator to send photocopies of the participant's medical records to GSK in lieu of completion of the GSK /AE/SAE CRF page.
- There may be instances when copies of medical records for certain cases are requested by GSK. In this case, all participant identifiers, with the exception of the participant number, will be redacted on the copies of the medical records before submission to GSK.
- The investigator will attempt to establish a diagnosis of the event based on signs, symptoms, and/or other clinical information. Whenever possible, the diagnosis (not the individual signs/symptoms) will be documented as the AE/SAE.

Assessment of Intensity

The investigator will make an assessment of intensity for each AE and SAE reported during the study and assign it to 1 of the following categories:

- **Mild:** An event that is easily tolerated by the participant, causing minimal discomfort and not interfering with everyday activities.
- **Moderate:** An event that causes sufficiently discomfort and interferes with normal everyday activities.
- **Severe:** An event that prevents normal everyday activities. An AE that is assessed as severe should not be confused with an SAE. Severe is a category utilized for rating the intensity of an event; and both AE and SAE can be assessed as severe.

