An event is defined as 'serious' when it meets at least 1 of the predefined outcomes as described in the definition of an SAE, NOT when it is rated as severe.

Assessment of Causality

- The investigator is obligated to assess the relationship between study treatment and each occurrence of each AE/SAE.
- A "reasonable possibility" of a relationship conveys that there are facts, evidence, and/or arguments to suggest a causal relationship, rather than a relationship cannot be ruled out.

- The investigator will use clinical judgment to determine the relationship.
- Alternative causes, such as underlying disease(s), concomitant therapy, and other risk factors, as well as the temporal relationship of the event to study treatment administration will be considered and investigated.
- The investigator will also consult the Investigator's Brochure (IB) and/or Product Information, for marketed products, in his/her assessment.
- For each AE/SAE, the investigator **must** document in the medical notes that he/she has reviewed the AE/SAE and has provided an assessment of causality.
- There may be situations in which an SAE has occurred and the investigator has minimal information to include in the initial report to GSK. However, **it is very important that the investigator always make an assessment of causality for every event before the initial transmission of the SAE data to GSK.**
- The investigator may change his/her opinion of causality in light of follow-up information and send an SAE follow-up report with the updated causality assessment.
- The causality assessment is one of the criteria used when determining regulatory reporting requirements.

Follow-up of AE and SAE

- The investigator is obligated to perform or arrange for the conduct of supplemental measurements and/or evaluations as medically indicated or as requested by GSK to elucidate the nature and/or causality of the AE or SAE as fully as possible. This may include additional laboratory tests or investigations, histopathological examinations, or consultation with other health care professionals. If a participant dies during participation in the study or during a recognized follow-up period, the investigator will provide GSK with a copy of any post-mortem findings including histopathology.
- New or updated information will be recorded in the originally completed CRF.
- The investigator will submit any updated SAE data to GSK within 24 hours of receipt of the information.

Reporting of SAE to GSK

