7. PRIMARY STATISTICAL ANALYSES

7.1. Safety Analyses of CAB LA

Four study phases are defined for this study: screening phase, oral phase, injection phase and follow-up phase (see [Appendix 4](#) for the definition of each phase).

The primary safety analysis will be conducted after all ongoing participants complete the Week 41 visit and datasets have been authorized. All data from injected participants collected from Week 5 to Week 41 (i.e., in the injection phase) will be analysed. Analysis endpoints will include Grade 2 or higher clinical and laboratory events that occur from the initial injection to 8 weeks after the last injection among participants who receive at least one injection.

The extended safety analysis will be conducted after all ongoing participants complete the Week 89 visit and datasets have been authorized. All data from injected participants collected from Week 5 to Week 89 (i.e., in the injection phase and the follow-up phase) will be analysed. Analysis endpoints are the same as in the primary safety analysis.

To assess safety, the number and the percent of participants experiencing each safety endpoint will be tabulated. Each participant will contribute once in each category (i.e., only for the highest severity AE) for the evaluation of safety.

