7.1.2. Adverse Events

Adverse events will be tabulated using MedDRA (v20.0 or above) system organ class (SOC) and preferred terms (PT), or preferred terms alone, by study phase. The number and percentage of participants experiencing each specific AEs (Grade 2 or higher, All AEs, SAEs, AEs leading to permanent treatment discontinuation or study withdrawal) will be tabulated. Number of subjects in the safety population who entered the study phase will be used as denominator in the calculation of percentages.

Drug-related AEs, SAEs, and Grade 2-4 AEs will also be tabulated. Any AE is assumed to be study treatment-related if relationship is marked 'YES' on CRF or value is missing. In addition, a summary table will be created for AEs by maximum severity by study phase. Common AEs are defined as AEs occurring in $\geq 5\%$ subjects during the study (based on preferred term). Common AEs, common non-serious AEs, common Grade 2-4 AEs, and common drug-related Grade 2-4 AEs will be tabulated.

All AE tables will be presented in a decreasing frequency order of SOC or PT unless otherwise specified.

[Table 4](#) provides an overview of the planned AE analyses, with full details of data displays being presented in [Appendix 14](#): List of Data Displays.

Table 4 Overview of Planned AE Analyses

Display Type	Data Displays Generated						
	Stats Analysis			Summary		Individual	
	T	F	L	T	F	F	L
AE Analyses							
All AEs				Y			Y
Grade 2 or higher AEs				Y			Y
SAEs				Y			Y
AE leading to treatment discontinuation or study withdrawal				Y			Y
Drug-related AEs				Y			
Drug-related SAEs				Y			
Drug-related Grade 2 or higher AEs				Y			
Common AEs				Y			
Common non-serious AEs				Y			
Common Grade 2-4 AEs				Y			
Common drug-related Grade 2-4 AEs				Y			

NOTES:

- T = Table, F = Figure, L = Listing, Y = Yes display generated.
- Stats Analysis = Represents TFL related to any formal statistical analyses (i.e. modelling) conducted.
- Summary = Represents TFL related to any summaries (i.e. descriptive statistics) of the observed raw data.
- Individual = Represents FL related to any displays of individual subject observed raw data.

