10.4.2.1. Treatment States for AE Data

Treatment State	Definition
Screening Phase	AE Start Date < Date of First Oral CAB
On-Oral CAB-Treatment	Day 1 ≤ AE Start Date ≤ Date of First CAB LA Injection – 1; for subjects who withdraw from oral CAB treatment, Day 1 ≤ AE Start Date ≤ Withdrawal date + 7 days
On-CAB LA-treatment	Date of First CAB LA Injection ≤ AE Start Date ≤ Date of Week 41 Visit ; for subjects who withdraw from CAB LA injection, Date of First CAB LA Injection ≤ AE Start Date ≤ Date of Last CAB LA Injection + 8 Weeks
Post-Treatment	AE Start Date > Date of Last CAB LA Injection + 8 weeks
Onset Time Since 1 st Dose (Days)	If Date of First Oral CAB (or CAB LA injection) >AE Onset Date, duration = AE Onset Date - Treatment Start Date If Date of First Oral CAB (or CAB LA injection) ≤ AE Onset Date, duration = AE Onset Date - Treatment Start Date +1 Missing otherwise.
AE Duration (Days)	AE Resolution Date – AE Onset Date + 1
Drug-related	If relationship is marked 'YES' on CRF OR value is missing

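### AEs are assigned to oral CAB or CAB LA by start date alone, so a clinical AE that worsens after the first injection can drop out of the injection-phase AE tables

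*Protocol*

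**What the plan says.** **Recording (Protocol Appendix 4, Section 12.4).** The investigator rates the intensity of each AE and must "assign it to 1 of the following categories". Follow-up is covered by a general sentence: "New or updated information will be recorded in the originally completed CRF". Neither place mentions a change of grade. The list of events that count as AEs includes "Exacerbation of a chronic or intermittent pre-existing condition including either an increase in frequency and/or intensity of the condition", but does not say whether this covers an event that itself began on study drug.

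**Assignment (SAP 10.4.2.1).** The oral state is "Day 1 ≤ AE Start Date ≤ Date of First CAB LA Injection – 1". The CAB LA state is "Date of First CAB LA Injection ≤ AE Start Date ≤ Date of Week 41 Visit", with a variant for men who stop injections early. Both use the start date, and neither has a branch for worsening.

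**Tabulation (SAP 7.1 and 7.1.2).** "Each participant will contribute once in each category (i.e., only for the highest severity AE) for the evaluation of safety". In addition, "a summary table will be created for AEs by maximum severity by study phase". SAP 7.1 defines the primary safety endpoint as clinical and laboratory events of Grade 2 and above in the window from first injection to eight weeks past the last.

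**Protocol intent (10.3.1.1.2).** "AEs will be summarized for those that are treatment emergent during LA dosing separately from those that are treatment emergent during oral dosing". A third summary combines the two. The protocol does not define treatment emergent or say whether it includes worsening.

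Both SAP versions in the file carry the same text on these points.

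**The concern.** The study separates the oral lead-in from the injections so that toxicity can be attributed to the right formulation. An AE that begins mildly on oral CAB and becomes clinically important only under the long-acting drug bears directly on the primary safety question. A rule based on start date and record-level maximum severity can attribute that worsening to the oral lead-in.

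Such carry-over is foreseeable. Protocol Appendix 8 lets a man with Grade 1 rash continue study drug under stated conditions, while Grade 3 rash ends treatment. If a rash started on oral CAB and reached Grade 3 after an injection, it would be tabulated by AE term as an oral-phase Grade 3 event and an oral-phase AE leading to discontinuation. AE withdrawals are part of the primary CAB LA endpoint, and no laboratory table would bring the rash back into the injection phase.

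**Working it through.** The plan states no figure to reproduce, so the check applies the classification rule to one case and then works out what one case weighs.

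**Inputs.** First injection on Day 35 (Protocol Schedule of Activities). 40 men planned for injection (Protocol 10.1.2) and about 48 for the oral phase (Protocol 5.2). The illustrative AE is an assumption: Grade 1 on Day 20, rising to Grade 3 on Day 45.

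**Step 1: apply SAP 10.4.2.1 with maximum severity per record.**

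| Recording | Oral phase | Injection phase |
|---|---|---|
| One updated record (start Day 20, Grade 3) | Grade 3 | no event |
| New record at worsening (Day 20 Grade 1; Day 45 Grade 3) | Grade 1 | Grade 3 |

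The same course gives opposite attributions, and the documents do not say which form of recording applies.

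**Step 2: compare with the laboratory rule.** SAP 7.1.3 takes the maximum laboratory grade within each study phase. A bilirubin rise that crosses the first injection could therefore appear as Grade 3 in the injection-phase laboratory table while its AE record stays in the oral phase. Clinical AEs have no equivalent within-phase rule.

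**Step 3: identify what moves.**
- Affected: the injection-phase AE tables by preferred term, by maximum grade, by drug-relatedness and for AEs leading to discontinuation.
- Not affected: laboratory grade tables; injection site reactions, which cannot precede an injection; the listings; the combined oral plus LA summary; and the proportion stopping injections in SAP 7.2, which counts every injected man who stops because of an AE, whatever its start date.

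**Step 4: weight of one man.**
- Injection-phase preferred-term row: 1/40 = 2.5 points, if he has no other injection-phase record under that term. The Clopper-Pearson 95% interval for 1/40 is 0.06% to 13.2%. For 2/40 = 5.0% it is 0.6% to 16.9%.
- Oral-phase Grade 2+ row: at most 1/48 = 2.1 points, and nothing if the AE was already Grade 2 on oral CAB.
- Overall injection-phase Grade 2+ rate: each man counts once, so it moves only if he has no other injection-phase Grade 2+ event. In the US study described in Protocol 3.2, 80% of the CAB LA group had a Grade 2 or higher AE in the injection phase. If that held here and were independent of carry-over (both assumptions, and the regimen differed), the expected shift per affected man would be (1 − 0.80) × 2.5 = 0.5 points.

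**Step 5: the other end of the phase.** The Week 41 tables are produced after a database freeze (SAP 3.2). An AE that starts in the injection phase and is upgraded during follow-up cannot change them. The same tables are produced again at Week 89 (SAP 10.14.5), and there the upgrade would raise the injection-phase grade.

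**The case against.** The strongest reply is that single-record entry is inferred. The follow-up sentence sits beside post-mortem findings and 24-hour SAE updates, and it names neither grade nor start date. The general AE definition in Appendix 4 covers exacerbated as well as new disease, and causality is assessed for every occurrence. The eCRF and its completion instructions are not in the file and may already deal with grade changes. This stands: one-record entry is likely, given a single intensity per AE and updates sent to the existing form, but it is not compelled.

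A second reply is that the AE tables are by study phase, and SAP 10.4.1 defines phases by date of occurrence rather than AE start date. This softens the point without removing it. The only AE dates that the SAP derivations use are onset and resolution, so a single updated record supplies no date of worsening to either section.

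A third reply is that much of the primary safety analysis does not depend on AE start dates. That is correct, and it confines the point to clinical AEs in the AE tables.

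The Week 4 safety check and the one-week gap before the first injection may also reduce carry-over, but the documents do not say by how much.

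**Conclusion.** The SAP assigns AEs by start date with no provision for worsening, and the protocol leaves the recording of a grade increase open. If sites keep one record, a clinical AE that begins on oral CAB and rises to Grade 2+ after the first injection is attributed to the wrong phase and is absent from the injection-phase AE tables. That conflicts with an endpoint defined by events occurring from the first injection. If sites differ in practice, attribution depends on site habit.

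The size is 2.5 points per affected man on a preferred-term row, and usually less on the overall Grade 2+ rate. The documents give no frequency of carry-over or worsening, so no total bias can be estimated.

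Three stronger readings are tempting and are not supported:
- A reader might infer that the primary injection-phase analysis misses such events altogether. Laboratory grades and the injection-discontinuation proportion still capture their part.
- A reader might infer that the protocol orders worsening into the existing record, or limits exacerbation to pre-existing conditions. The text does neither.
- A reader might infer that later upgrading alters the Week 41 result. It can alter only the Week 89 rerun.

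**What to change.** 1. **CRF completion instructions.** When an ongoing AE increases in grade after the first CAB LA injection, or after the end of the injection phase, require either a dated grade change or a new linked AE record with its own start date and grade. First check whether the current eCRF already captures this.
2. **SAP 10.4.2.1 and 7.1.2.** Count an AE as emergent in the phase in which it starts or increases in grade, and tabulate it at the maximum grade reached within that phase. This extends to AEs the rule that SAP 7.1.3 already uses for laboratory data, and it gives the protocol's undefined term a meaning.
3. **AEs leading to discontinuation.** Apply the same rule.

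The cost is one site instruction and a short SAP amendment. The downside is a few linked records. They would inflate the occurrence counts in Tables 2.7 and 2.13 and shorten AE duration, so the SAP should say that linked records are collapsed for those outputs.

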12.6. Appendix 6: Liver Safety: Required Actions and Follow-up Assessments

Phase 1 Liver chemistry stopping criteria have been designed to assure participant safety and to evaluate liver event etiology (in alignment with FDA premarketing clinical liver safety guidance).

<http://www.fda.gov/downloads/Drugs/GuidanceComplianceRegulatoryInformation/Guidances/UCM174090.pdf>

Phase 1 liver chemistry stopping criteria and required follow up assessments

Liver Chemistry Stopping Criteria	
ALT-absolute	
ALT\geq3xULN
 
If ALT\geq3xULN AND bilirubin^{1,2} \geq 2xULN (>35% direct bilirubin) or INR >1.5, Report as an SAE.
 
See additional Actions and Follow Up Assessments listed below

Required Actions and Follow up Assessments	
Actions	Follow Up Assessments

 • Immediately discontinue study treatment • Report the event to GSK within 24 hours • Complete the liver event CRF, and complete an SAE data collection tool if the event also meets the criteria for an SAE² • Perform liver event follow up assessments • Monitor the participant until liver chemistries resolve, stabilize, or return to within baseline (see MONITORING below) 
MONITORING:
 
If ALT\geq3xULN AND bilirubin \geq 2xULN or INR >1.5
 
 • Repeat liver chemistries (include ALT, AST, alkaline phosphatase, bilirubin) and perform liver event follow up assessments within 24 hrs • Monitor participants twice weekly until liver chemistries resolve, stabilize or return to within baseline • A specialist or hepatology consultation is 	
 • Viral hepatitis serology³ • Obtain INR and recheck with each liver chemistry assessment until the transaminases values show downward trend • A blood sample for pharmacokinetic (PK) analysis will be obtained at every visit, and therefore, should be available to match with Liver Function Test (LFT) findings. An additional PK sample should be obtained at the same time as any unscheduled LFT assessment. • Serum creatine phosphokinase (CPK) and lactate dehydrogenase (LDH). • Fractionate bilirubin, if total bilirubin\geq2xULN • Obtain complete blood count with differential to assess eosinophilia • Record the appearance or worsening of clinical symptoms of liver injury, or hypersensitivity e.g., fatigue, decreased appetite, nausea, vomiting, abdominal

Liver Chemistry Stopping Criteria	

recommended
 
If ALT\geq3xULN AND bilirubin < 2xULN and INR \leq1.5:
 
 Repeat liver chemistries (include ALT, AST, alkaline phosphatase, bilirubin) and perform liver event follow up assessments within 24-72 hrs Monitor participants weekly until liver chemistries resolve, stabilize or return to within baseline 	
pain, jaundice, fever, or rash, on the AE report form
 
 Record use of concomitant medications on the concomitant medications report form including acetaminophen, herbal remedies, other over the counter medications. Record alcohol use on the liver event alcohol intake case report form 
If ALT\geq3xULN AND bilirubin \geq 2xULN or INR >1.5:
 
 Anti-nuclear antibody, anti-smooth muscle antibody, Type 1 anti-liver kidney microsomal antibodies, and quantitative total immunoglobulin G (IgG) or gamma globulins. Liver imaging (ultrasound, magnetic resonance, or computerized tomography) and /or liver biopsy to evaluate liver disease; complete Liver Imaging and/or Liver Biopsy CRF forms.

- Serum bilirubin fractionation should be performed if testing is available. If serum bilirubin fractionation is not immediately available, discontinue study treatment for that participant if ALT \geq 3xULN and bilirubin \geq 2xULN. Additionally, if serum bilirubin fractionation testing is unavailable, record presence of detectable urinary bilirubin on dipstick, indicating direct bilirubin elevations and suggesting liver injury.
- All events of ALT \geq 3xULN and bilirubin \geq 2xULN (>35% direct bilirubin) or ALT \geq 3xULN and INR>1.5, if INR measured, which may indicate severe liver injury (possible 'Hy's Law'), must be reported as an SAE (excluding studies of hepatic impairment or cirrhosis); INR measurement is not required and the threshold value stated will not apply to participants receiving anticoagulants
- Hepatitis A IgM antibody; Hepatitis B surface antigen and Hepatitis B Core Antibody (IgM); Hepatitis C RNA; Cytomegalovirus IgM antibody; Epstein-Barr viral capsid antigen IgM antibody (or if unavailable, obtain heterophile antibody or monospot testing); Hepatitis E IgM antibody
- Record the date/time of the PK blood sample draw and the date/time of the last dose of study treatment prior to PK blood sample draw on the CRF. If the date or time of the last dose is unclear, provide the participant's best approximation. If the date/time of the last dose cannot be approximated OR a PK sample cannot be collected in the time period indicated above, do not obtain a PK sample. Instructions for sample handling and shipping are in the SRM.

References

12.7. Appendix 7: Division of AIDS Table for Grading the Severity of Adult and Pediatric Adverse Events Version 2.1, March 2017

VERSION 2.1, March 2017

The Division of AIDS Table for Grading the Severity of Adult and Pediatric Adverse Events (“DAIDS AE Grading Table”) is a descriptive terminology which can be utilised for Adverse Event (AE) reporting. A grading (severity) scale is provided for each AE term.

Estimating Severity Grade for Parameters Not Identified in the Grading Table

The functional table below should be used to grade the severity of an AE that is not specifically identified in the grading table. In addition, all deaths related to an AE are to be classified as grade 5

PARAMETER	GRADE 1 MILD	GRADE 2 MODERATE	GRADE 3 SEVERE	GRADE 4 POTENTIALLY LIFE- THREATENING
Clinical adverse event NOT identified elsewhere in the grading table	Mild symptoms causing no or minimal interference with usual social & functional activities with intervention not indicated	Moderate symptoms causing greater than minimal interference with usual social & functional activities with intervention indicated	Severe symptoms causing inability to perform usual social & functional activities with intervention or hospitalization indicated	Potentially life-threatening symptoms causing inability to perform basic self-care functions with intervention indicated to prevent permanent impairment, persistent disability, or death

Major Clinical Conditions

Cardiovascular

PARAMETER	GRADE 1 MILD	GRADE 2 MODERATE	GRADE 3 SEVERE	GRADE 4 POTENTIALLY LIFE- THREATENING
Arrhythmia (by ECG or physical examination) Specify type, if applicable	No symptoms AND No intervention indicated	No symptoms AND Non-urgent intervention indicated	Non-life-threatening symptoms AND Non-urgent intervention indicated	Life-threatening arrhythmia OR Urgent intervention indicated

PARAMETER	GRADE 1 MILD	GRADE 2 MODERATE	GRADE 3 SEVERE	GRADE 4 POTENTIALLY LIFE- THREATENING
Blood Pressure Abnormalities¹ Hypertension (with the lowest reading taken after repeat testing during a visit) ≥ 18 years of age	140 to < 160 mmHg systolic OR 90 to < 100 mmHg diastolic	≥ 160 to < 180 mmHg systolic OR ≥ 100 to < 110 mmHg diastolic	≥ 180 mmHg systolic OR ≥ 110 mmHg diastolic	Life-threatening consequences in a participant not previously diagnosed with hypertension (e.g., malignant hypertension) OR Hospitalization indicated
< 18 years of age	> 120/80 mmHg	$\geq 95^{\text{th}}$ to < 99 th percentile + 5 mmHg adjusted for age, height, and gender (systolic and/or diastolic)	$\geq 99^{\text{th}}$ percentile + 5 mmHg adjusted for age, height, and gender (systolic and/or diastolic)	Life-threatening consequences in a participant not previously diagnosed with hypertension (e.g., malignant hypertension) OR Hospitalization indicated
Hypotension	No symptoms	Symptoms corrected with oral fluid replacement	Symptoms AND IV fluids indicated	Shock requiring use of vasopressors or mechanical assistance to maintain blood pressure
Cardiac Ischemia or Infarction Report only one	NA NA	NA	New symptoms with ischemia (stable angina) OR New testing consistent with ischemia	Unstable angina OR Acute myocardial infarction
Heart Failure	No symptoms AND Laboratory or cardiac imaging abnormalities	Symptoms with mild to moderate activity or exertion	Symptoms at rest or with minimal activity or exertion (e.g., hypoxemia) OR Intervention indicated (e.g., oxygen)	Life-threatening consequences OR Urgent intervention indicated (e.g., vasoactive medications, ventricular assist device, heart transplant)

¹ Blood pressure norms for children < 18 years of age can be found in: Expert Panel on Integrated Guidelines for Cardiovascular Health and Risk Reduction in Children and Adolescents. Pediatrics 2011;128;S213; originally published online November 14, 2011; DOI: 10.1542/peds.2009-2107C

Cardiovascular

PARAMETER	GRADE 1 MILD	GRADE 2 MODERATE	GRADE 3 SEVERE	GRADE 4 POTENTIALLY LIFE- THREATENING
Hemorrhage (with significant acute blood loss)	NA	Symptoms AND No transfusion indicated	Symptoms AND Transfusion of ≤ 2 units packed RBCs indicated	Life-threatening hypotension OR Transfusion of > 2 units packed RBCs (for children, packed RBCs > 10 cc/kg) indicated
Prolonged PR Interval or AV Block Report only one > 16 years of age	PR interval 0.21 to < 0.25 seconds	PR interval ≥ 0.25 seconds OR Type I 2 nd degree AV block	Type II 2 nd degree AV block OR Ventricular pause ≥ 3.0 seconds	Complete AV block
≤ 16 years of age	1 st degree AV block (PR interval > normal for age and rate)	Type I 2 nd degree AV block	Type II 2 nd degree AV block OR Ventricular pause ≥ 3.0 seconds	Complete AV block
Prolonged QTc Interval²	0.45 to 0.47 seconds	> 0.47 to 0.50 seconds	> 0.50 seconds OR ≥ 0.06 seconds above baseline	Life-threatening consequences (e.g., Torsade de pointes, other associated serious ventricular dysrhythmia)
Thrombosis or Embolism Report only one	NA	Symptoms AND No intervention indicated	Symptoms AND Intervention indicated	Life-threatening embolic event (e.g., pulmonary embolism, thrombus)

² As per Bazett's formula

Dermatologic

PARAMETER	GRADE 1 MILD	GRADE 2 MODERATE	GRADE 3 SEVERE	GRADE 4 POTENTIALLY LIFE- THREATENING
Alopecia (scalp only)	Detectable by study participant, caregiver, or physician AND Causing no or minimal interference with usual social & functional activities	Obvious on visual inspection AND Causing greater than minimal interference with usual social & functional activities	NA	NA
Bruising	Localized to one area	Localized to more than one area	Generalized	NA
Cellulitis	NA	Non-parenteral treatment indicated (e.g., oral antibiotics, antifungals, antivirals)	IV treatment indicated (e.g., IV antibiotics, antifungals, antivirals)	Life-threatening consequences (e.g., sepsis, tissue necrosis)
Hyperpigmentation	Slight or localized causing no or minimal interference with usual social & functional activities	Marked or generalized causing greater than minimal interference with usual social & functional activities	NA	NA
Hypopigmentation	Slight or localized causing no or minimal interference with usual social & functional activities	Marked or generalized causing greater than minimal interference with usual social & functional activities	NA	NA
Petechiae	Localized to one area	Localized to more than one area	Generalized	NA

PARAMETER	GRADE 1 MILD	GRADE 2 MODERATE	GRADE 3 SEVERE	GRADE 4 POTENTIALLY LIFE- THREATENING
Pruritus ³ (without skin lesions)	Itching causing no or minimal interference with usual social & functional activities	Itching causing greater than minimal interference with usual social & functional activities	Itching causing inability to perform usual social & functional activities	NA
Rash Specify type, if applicable	Localized rash	Diffuse rash OR Target lesions	Diffuse rash AND Vesicles or limited number of bullae or superficial ulcerations of mucous membrane limited to one site	Extensive or generalized bullous lesions OR Ulceration of mucous membrane involving two or more distinct mucosal sites OR Stevens-Johnson syndrome OR Toxic epidermal necrolysis

³ For pruritus associated with injections or infusions, see the *Site Reactions to Injections and Infusions* section (page 23 in source DAIDS Table).

Endocrine and Metabolic

PARAMETER	GRADE 1 MILD	GRADE 2 MODERATE	GRADE 3 SEVERE	GRADE 4 POTENTIALLY LIFE- THREATENING
Diabetes Mellitus	Controlled without medication	Controlled with medication OR Modification of current medication regimen	Uncontrolled despite treatment modification OR Hospitalization for immediate glucose control indicated	Life-threatening consequences (e.g., ketoacidosis, hyperosmolar non-ketotic coma, end organ failure)
Gynecomastia	Detectable by study participant, caregiver, or physician AND Causing no or minimal interference with usual social & functional activities	Obvious on visual inspection AND Causing pain with greater than minimal interference with usual social & functional activities	Disfiguring changes AND Symptoms requiring intervention or causing inability to perform usual social & functional activities	NA

PARAMETER	GRADE 1 MILD	GRADE 2 MODERATE	GRADE 3 SEVERE	GRADE 4 POTENTIALLY LIFE- THREATENING
Hyperthyroidism	No symptoms AND Abnormal laboratory value	Symptoms causing greater than minimal interference with usual social & functional activities OR Thyroid suppression therapy indicated	Symptoms causing inability to perform usual social & functional activities OR Uncontrolled despite treatment modification	Life-threatening consequences (e.g., thyroid storm)
Hypothyroidism	No symptoms AND Abnormal laboratory value	Symptoms causing greater than minimal interference with usual social & functional activities OR Thyroid replacement therapy indicated	Symptoms causing inability to perform usual social & functional activities OR Uncontrolled despite treatment modification	Life-threatening consequences (e.g., myxedema coma)
Lipoatrophy⁴	Detectable by study participant, caregiver, or physician AND Causing no or minimal interference with usual social & functional activities	Obvious on visual inspection AND Causing greater than minimal interference with usual social & functional activities	Disfiguring changes	NA
Lipohypertrophy⁵	Detectable by study participant, caregiver, or physician AND Causing no or minimal interference with usual social & functional activities	Obvious on visual inspection AND Causing greater than minimal interference with usual social & functional activities	Disfiguring changes	NA

⁴ Definition: A disorder characterized by fat loss in the face, extremities, and buttocks.

⁵ Definition: A disorder characterized by abnormal fat accumulation on the back of the neck, breasts, and abdomen

Gastrointestinal

PARAMETER	GRADE 1 MILD	GRADE 2 MODERATE	GRADE 3 SEVERE	GRADE 4 POTENTIALLY LIFE- THREATENING
Anorexia	Loss of appetite without decreased oral intake	Loss of appetite associated with decreased oral intake without significant weight loss	Loss of appetite associated with significant weight loss	Life-threatening consequences OR Aggressive intervention indicated (e.g., tube feeding, total parenteral nutrition)
Ascites	No symptoms	Symptoms AND Intervention indicated (e.g., diuretics, therapeutic paracentesis)	Symptoms recur or persist despite intervention	Life-threatening consequences
Bloating or Distension Report only one	Symptoms causing no or minimal interference with usual social & functional activities	Symptoms causing greater than minimal interference with usual social & functional activities	Symptoms causing inability to perform usual social & functional activities	NA
Cholecystitis	NA	Symptoms AND Medical intervention indicated	Radiologic, endoscopic, or operative intervention indicated	Life-threatening consequences (e.g., sepsis, perforation)
Constipation	NA	Persistent constipation requiring regular use of dietary modifications, laxatives, or enemas	Obstipation with manual evacuation indicated	Life-threatening consequences (e.g., obstruction)
Diarrhea ≥ 1 year of age	Transient or intermittent episodes of unformed stools OR Increase of ≤ 3 stools over baseline	Persistent episodes of unformed to watery stools OR Increase of 4 to 6 stools over baseline per 24-hour period	Increase of ≥ 7 stools per 24-hour period OR IV fluid replacement indicated	Life-threatening consequences (e.g., hypotensive shock)

PARAMETER	GRADE 1 MILD	GRADE 2 MODERATE	GRADE 3 SEVERE	GRADE 4 POTENTIALLY LIFE- THREATENING
< 1 year of age	Liquid stools (more unformed than usual) but usual number of stools	Liquid stools with increased number of stools OR Mild dehydration	Liquid stools with moderate dehydration	Life-threatening consequences (e.g., liquid stools resulting in severe dehydration, hypotensive shock)
Dysphagia or Odynophagia Report only one and specify location	Symptoms but able to eat usual diet	Symptoms causing altered dietary intake with no intervention indicated	Symptoms causing severely altered dietary intake with intervention indicated	Life-threatening reduction in oral intake
Gastrointestinal Bleeding	Not requiring intervention other than iron supplement	Endoscopic intervention indicated	Transfusion indicated	Life-threatening consequences (e.g., hypotensive shock)
Mucositis or Stomatitis Report only one and specify location	Mucosal erythema	Patchy pseudomembranes or ulcerations	Confluent pseudomembranes or ulcerations OR Mucosal bleeding with minor trauma	Life-threatening consequences (e.g., aspiration, choking) OR Tissue necrosis OR Diffuse spontaneous mucosal bleeding
Nausea	Transient (< 24 hours) or intermittent AND No or minimal interference with oral intake	Persistent nausea resulting in decreased oral intake for 24 to 48 hours	Persistent nausea resulting in minimal oral intake for > 48 hours OR Rehydration indicated (e.g., IV fluids)	Life-threatening consequences (e.g., hypotensive shock)
Pancreatitis	NA	Symptoms with hospitalization not indicated	Symptoms with hospitalization indicated	Life-threatening consequences (e.g., circulatory failure, hemorrhage, sepsis)
Perforation (colon or rectum)	NA	NA	Intervention indicated ^P	Life-threatening consequences

